#### 12.1.4 Handling of Missing Values and of Values Outside the Detection Limits

For periodontal parameters:

- Six sites per tooth are to be evaluated. At least 4 of the 6 sites per tooth must be evaluated and have the measurements recorded for the tooth to be included in the

#### Confidentiality Statement

---

Data and information contained in this document are considered to constitute trade secrets and confidential commercial information, and the legal protections provided to such trade secrets and confidential information are hereby claimed under the applicable provisions of applicable law. No part of this document may be publicly disclosed without the written consent of Philip Morris Products S.A.

---

assessment. If the site is evaluated and there is no PD to measure, the site must be recorded as 0 to indicate that there was no PD at the site (and to distinguish it from a site that was not evaluated). When less than 4 sites are recorded, the assessment of the tooth will be considered as missing, and the values will be excluded from the calculation of the means.

For BoExp parameters:

- Values below the lower limit of quantification (LLOQ) will be imputed using LLOQ/2. For values above the upper limit of quantification (ULOQ), the ULOQ will be imputed.
- The number of values below LLOQ or above ULOQ will be presented in each summary table. If more than 50% of the data are below LLOQ, only the number and percentage of values below LLOQ will be reported in the summary together with the minimum and maximum values.

For self-reported tobacco or nicotine containing tobacco product use over the duration of the study data:

- Only available data will be included in the product use summaries.
- Overall product exposure groups will be defined based on the data collected from randomization until EOS.

Further details will be provided in the SAP.

### 12.1.5 Significance Level for Inferential Analysis

The primary analysis, of PD at 6 months will be tested using a one-sided alpha level of 2.5%.

1. PD at 6 months will be tested.

The secondary analysis of PD at 3 months and CAL at 6 and 3 months will be tested in a hierarchical manner, using a one-sided alpha level of 2.5%, depending on the outcome of the test at previously specified endpoint in hierarchical testing order.

1. PD at 3 months will be tested only if the test for PD at 6 months is significant.
2. CAL at 6 months will be tested only if the test for PD at 3 months is significant
3. CAL at 3 months will be tested only if the test for CAL at 6 months is significant.

Additional analysis of the secondary endpoint, the BoExp will be tested, in a hierarchical manner within each BoExp (independent of the other statistical tests being performed), using a one-sided alpha level of 2.5%. The hierarchical order will be:

1. BoExp at 6 months will be tested.

### Confidentiality Statement

---

Data and information contained in this document are considered to constitute trade secrets and confidential commercial information, and the legal protections provided to such trade secrets and confidential information are hereby claimed under the applicable provisions of applicable law. No part of this document may be publicly disclosed without the written consent of Philip Morris Products S.A.

---

2. BoExp at 3 months will be tested only if the test for BoExp at 6 months is significant.

Total NNAL and CEMA levels (concentration data adjusted for creatinine), analyzed on a logarithmic scale, will be tested at 6 and then 3 months, in that order, so that the testing of each BoExp will stop if the test is not significant.

Unless stated otherwise, all statistical tests will be one-sided and conducted at the 2.5% level, and all CIs will be two-sided 95%.

## 12.2 Determination of Sample Size and Power Consideration

The patients will be randomized into 1 of 2 study groups: IQOS or cigarettes. Patients will be analyzed by their actual exposure throughout the course of the study. Therefore, there will be patients who predominantly use IQOS or patients who predominantly use cigarettes, however, there will also be patients who predominantly use other tobacco and nicotine containing tobacco products, or have a pattern of mixed tobacco product use. All patients will continue in the study but will be analyzed based on their exposure pattern during the study. Depending on the patterns of product use observed in the study, sensitivity analyses and descriptive summaries will be implemented.

The statistical hypothesis that will be tested for PD at 6 months is:

- $H_0: X_{IQOS} - X_{cigarette} \leq 0.$
- $H_A: X_{IQOS} - X_{cigarette} > 0.$

Where  $X_{IQOS}$  and  $X_{cigarette}$  are the adjusted mean changes from baseline values (baseline minus endline) of PD for IQOS and cigarettes, respectively. The  $H_0$  is rejected with a one-sided alpha level of 2.5%.

In the literature reviewed, the papers of Rosa [44] and Preshaw [43] are similar to the study described in this protocol, in that they include:

- Some requirements on minimum PD for inclusion
- Comparison of smokers with former smokers
- Means and SDs (or standard errors of the mean and sample size)

Therefore it is assumed that the cigarette arm will have similar results to what is described in the literature for current smokers and that the results in the IQOS arm will be similar to what is observed in former smokers.

Based on the published data and recommendations from the American clinical practice guidelines [85], the following estimates with PD differences and standard deviations between smokers and non-smokers (Table 7) are based on data assessed at 3, 9 and 12 months:

**Table 7 Sample sizes for PD differences between smokers and non-smokers and standard deviations based on the literature**

SD \ difference (mm)	0.2	0.25	0.3	0.35
	0.4	64	42	29
0.45	81	52	37	27
0.5	100	64	45	33

Abbreviation: SD = Standard deviation

Thus, the sample size selected above gives sufficient power for testing PD.

With alpha of 2.5%, power of 80%, SD of 0.5, and effect difference of 0.25 mm, then sample size needed in each arm is 64 patients. By considering 25% of drop out and product switching, 86 patients per arm, i.e., 172 patients in total, are needed.

### 12.3 Product use

[figure not shown]
Although patients are being requested to use solely the product allocated to their respective study arm, it is considered that not all patients randomized to the IQOS arm or to continue smoking cigarettes will exclusively use the randomized product at all times during the study. Patients may concomitantly use IQOS and cigarettes (dual-use). To assess dual use of IQOS and cigarettes, PMI has defined categories of pattern of product use.

Product use pattern categories will be specified based on the average number of product used per month of each category (i.e., Marlboro HeatSticks or smoked cigarettes) as self-reported in the product use questionnaire over the study duration. Further determinants, such as percentages of the respective products, or numbers of other nicotine-containing products may be used, and will be provided in the SAP.

Actual product use pattern categorization is described in Figure 3. Primary analysis will consider only those patients who used only HeatSticks and/or cigarettes. Those who used other nicotine-containing products (e.g., e-cigarettes) will be considered in a separate category, "Other" (not represented in Figure 3). More granular product exposure categories may be used for the detailed description of the product use patterns observed in the study. Full details of the product use categories will be reported in the SAP.

**Figure 3 Product Use Categorization**

Abbreviations: HS = Marlboro HeatSticks; cig = cigarette  
Details of the product use categories will be reported in the SAP.

## 12.4 Analysis Populations

The main population for non-safety analysis will be the As Exposed Set.

Safety will be analyzed using the Safety Set.

### 12.4.1 As Exposed Set

The As Exposed Set consists of all randomized patients who have at least one post-randomization product use experience, and who have at least one valid non-safety assessment after randomization. The As Exposed Set will be analyzed by actual exposure (product use pattern).

### 12.4.2 Full Analysis Set (FAS)

The Full Analysis Set (FAS) consists of all randomized patients who have at least one post-randomization product use experience, and who have at least one valid non-safety assessment after randomization. The FAS will be analyzed by randomized study product.

### 12.4.3 Per Protocol Set (PP)

The Per Protocol Set (PP) is the subset of the FAS who fulfill key compliance criteria of the protocol and have no major protocol deviation that influences the evaluability of the study data (to be further described in the SAP).

### 12.4.4 Adherent Use Set

The Adherent Use Set is the subset of the FAS who are adherent to their randomized study product.

### 12.4.5 Safety Set

The Safety Set consists of all patients enrolled with signed ICF who have at least one valid safety assessment during the course of the study. The Safety Set will be analyzed by actual exposure (product use pattern).

## 12.5 Demographics and Baseline Characteristics

The demographic variables will be summarized by product use pattern categories and by the randomization strata (daily cigarette consumption and disease severity) for the As Exposed Set. In addition, they will be summarized by randomization arm for the FAS and PP Sets. Data will be listed by randomization arm. No inferential analyses will be presented for the demographics and baseline characteristics.

## 12.6 Primary Analysis

The primary analysis evaluates the change from baseline in PD, which will be calculated for each patient across all sites with a baseline PD  $\geq 4$  mm, resulting in one value per patient per endpoint for each visit (baseline, Month 3 and 6).

The primary analysis will be performed on the As Exposed Set using a mixed model for repeated measurements (MMRM) for only subjects who have used cigarettes and/or Heatsticks. The model will include the PD change from baseline as the dependent variable, adjusting for daily cigarette consumption and disease severity at V1, full mouth PD at V1, exposure group and its interaction with visit. Site will be included as a random effect. The modeling assumptions will be evaluated and the model fit will be assessed by the analysis of the residual (diagnostics) and by comparing the values predicted vs. the observed values (calibration).

Additionally, the analysis will be performed on the FAS, PP and Adherent Use populations as a supportive sensitivity analysis. Additional sub group analyses such as for “Other” product use groups may be analyzed and will be defined in the SAP.

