**Sample Size:**

The sample size needed to attain 80% power to show at least a 0.25 mm gain of PD in IQOS compared to the cigarette arm, using a one-sided test with 2.5% type I error probability, assuming a dropout rate of 15% and a 10% rate of patients not-adherent to product allocation. A total of 172 patients (86 in each arm) are required to be randomized.

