### **Confidentiality Statement**

---

Data and information contained in this document are considered to constitute trade secrets and confidential commercial information, and the legal protections provided to such trade secrets and confidential information are hereby claimed under the applicable provisions of applicable law. No part of this document may be publicly disclosed without the written consent of Philip Morris Products S.A.

---

probably due to the vasoconstrictive action of nicotine on gingival vessels. Because IQOS delivers nicotine, but much reduced levels of other HPHCs, this study may help to differentiate the effects of nicotine vs the effects of HPHCs. To investigate this, it is planned to collect 1) GCF samples, to measure inflammatory components of this oral fluid when switching to IQOS compared to continuing using cigarettes, 2) buccal swabs, to perform an RNA profiling of those cells which are directly exposed to cigarette smoke or IQOS aerosol; and 3) SP samples, to assess the change of the oral microbiome when switching to IQOS compared to patients continuing using cigarettes. The analyses of GCF and buccal swabs will help to better understand the underlying mechanism of the diseases related to cigarette smoke.

The study will follow a two parallel arm randomization design with the following strata: 1) daily cigarette consumption over the month prior to V1 and 2) PD in smokers with generalized chronic periodontitis [78]. This selection is based on the fact that: 1) the degree of smoking exposure is related to the severity of periodontal destruction [25, 82] 2) pre-treatment depth of PD and CAL have been shown to affect response of therapy [83, 84].

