## 6.3 Method for Assigning Patients to Study Arms

After all assessments of V1 have been completed, patients will be randomized to 1 of the 2 study arms; continued cigarette smoking or IQOS use. Patients will be informed about their study arm allocation at V2. Randomization will be done through the Interactive Web and Voice Response System (IXRS) at any time during the visit. Patients will be randomized in one of the two study arms, IQOS arm:cigarette arm in a 1:1 ratio using a stratified randomization (based on daily cigarette consumption over the month (30 days) prior to V1 (10-19 cigarettes/day vs. >19 cigarettes/day), and disease severity (< 5 mm PD vs.  $\geq$  5 mm PD) in smokers with generalized chronic periodontitis. Disease severity is based on the tooth site having the most severe condition of PD [78]. In each arm, a quota will be applied to ensure that patients with PD  $\geq$  5 mm represent at least 50% of the randomized patients. Arm assignment for patients with PD < 5 mm will be capped at n = 80, after which enrollment of patients with PD < 5 mm will be stopped. Patients with PD < 5 mm already enrolled but not randomized may be discontinued in order to ensure that randomization quota are met. Enrollment of patients with PD  $\geq$  5 mm will continue until 172 patients are randomized. At this stage, patients' enrollment will be stopped and patients already enrolled but not randomized may be discontinued. In case patients are discontinued after V1, they will be referred to their dentist/general practitioner and will receive financial compensation for the

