### 7.6.2 Scaling and Root Planing (SRP)

First SRP will be performed on teeth with PD  $\geq 4$  mm by using Gracey Hand Curettes at V2. The following SRP treatments will be performed and recorded as “unscheduled” SRP visits. SRP treatments of teeth with PD  $< 4$  mm will be performed based on PI’s judgment, at the time he/she finds it necessary. All SRP treatments must be completed within 8 weeks after V2. If additional SRP visits need to be performed because of periodontitis worsening, based on Investigator’s judgement, they will be recorded as unscheduled visits, including the reason for this unplanned SRP.

PD, mobility and BOP before SRP will be measured as per the standard of care treatments at V2. These data will, however, not be reported in the CRF.

The order of SRP should be determined for individual patients. The identification of each tooth treated and the respective time of treatment should be recorded.

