9.5.1.1 Primary Analyses

Primary Analysis of Change from Baseline in PD at V4	
Population	
 • As Exposed Set For this analysis, subjects categorized in IQOS user, cigarette user or dual user will be included with initial PD \geq 4mm will be included.
	The primary analysis will be performed on the As Exposed Set using a mixed model for repeated measurements (MMRM). Estimates of difference in PD will be calculated for Cigarette User against IQOS User categories and Cigarette User against Dual User categories. The model will include the PD change from baseline as the dependent variable, adjusting for the following covariates; 
 1. Daily cigarette consumption at V1 2. Disease severity at V1 3. Full mouth PD at V1 4. Visit 5. Product use pattern (IQOS user, cigarette smoker or dual user) 6. Interaction between visit and product use

Confidentiality Statement

Data and information contained in this document are considered to constitute trade secrets and confidential commercial information, and the legal protections provided to such trade secrets and confidential information are hereby claimed under the provisions of applicable law. No part of this document may be publicly disclosed without the written consent of Philip Morris Products S.A

Primary Analysis of Change from Baseline in PD at V4

7. Average daily cigarette use at each visit
8. Interaction between Daily cigarette consumption at V1 and product use
9. Interaction between Disease severity at V1 and product use
10. Time since last SRP
11. Number of target tooth/teeth extracted
12. Number of non-measured target tooth/teeth extracted
13. Baseline tooth mobility

Site will be included as a random effect. The degrees of freedom will be adjusted by using Kenward Roger (KR) method. A Toeplitz structure (“type=toep”) will be specified as the covariance matrix. However, other covariance structures may be used in case of non-convergence. Covariates 8-12 will be assessed for adequacy in the model using a step-wise (backward) approach through the following algorithm.

1. Fit a full model using maximum likelihood with all covariates
2. Perform a likelihood ratio test for the full model and drop the covariate with the largest p-value for the likelihood ratio statistic if it is more than 0.05.
3. Drop one covariate (only covariates 7-14) and re-fit the model.

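### The primary MMRM fits one baseline pocket-depth slope for months 3 and 6, so the month-6 contrast is biased if that slope changes between visits and the product-use groups also differ in baseline depth

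*Protocol*

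**What the plan says.** Protocol 12.6 models PD change from baseline with daily cigarette consumption and disease severity at V1, and then "full mouth PD at V1, exposure group and its interaction with visit". The synopsis (Statistical Methods) also names only a treatment-by-visit interaction.

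SAP 9.5.1.1 lists 13 covariates. One involves visit, item 6: "Interaction between visit and product use". Items 8 and 9 let daily cigarette consumption at V1 and disease severity at V1 interact with product use, not with visit, and both are candidates for backward selection. Item 10 is time since the last scaling and root planing (SRP), a droppable main effect. The sample code writes out only visit and visit by exposure. The covariance is Toeplitz, which implies equal variance at the two visits. A closing note allows further covariates but names none.

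The groups in the primary analysis are defined by actual product use (protocol 12.4.1, SAP 8.1). Protocol 4.1 says that "pre-treatment depth of PD and CAL have been shown to affect response of therapy".

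**The concern.** The confirmatory result is the month-6 difference between use groups, and it decides whether PD at 3 months and then clinical attachment level (CAL) may be tested (protocol 12.1.5, SAP 9.1.8). Use groups can differ in baseline depth, and the protocol itself regards depth as prognostic. A model with one slope for both visits adjusts month 6 partly with the month-3 relation.

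The schedule gives a reason to doubt that the two relations are equal. Protocol 7.6.2 states: "All SRP treatments must be completed within 8 weeks after V2". With 30-day months (protocol 4.3), V3 falls on days 83 to 97 and V4 on days 166 to 194. A patient whose last SRP is on day 56 has had 27 to 41 days of healing at V3, against 110 to 138 at V4.

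At stake is a small systematic shift in the primary estimate, in either direction, that the data already collected could remove.

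**Working it through.** **1. The plan's own figure.** Protocol 12.2: "With alpha of 2.5%, power of 80%, SD of 0.5, and effect difference of 0.25 mm"; the synopsis adds "using a one-sided test with 2.5% type I error probability". The normal approximation is n = 2 × (1.960 + 0.842)² × (0.5/0.25)² = 62.8, so 63 per group; the noncentral t gives 64, as stated. Then 64/(1 − 0.25) = 85.3, so 86 per arm and 172 in total, as stated ("By considering 25% of drop out and product switching, 86 patients per arm"). The calculation uses no covariate model.

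**2. What the single slope does.** Let b3 and b6 be the true slopes of PD reduction on baseline depth, and d the difference in mean baseline depth between two use groups. Take complete data, equal variance at both visits and a free group effect at each visit.
- The sum of the two visits carries all the information on the common slope, so the fitted slope is (b3 + b6)/2.
- The difference between the visits contains no baseline term, so its group contrast keeps (b6 − b3) × d.
- The month-6 contrast is half the sum plus half the difference. Its bias is therefore **(b6 − b3)/2 × d**, whatever the within-patient correlation.

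**3. Size.** Neither document gives b6 − b3 or d, so both are assumed. The standard error is 0.5 × √(2/64) = 0.088 mm. The type I error is for bias in favour of IQOS; power at 0.25 mm (0.807 without bias) is for bias against it.

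| Slope gap (mm per mm) | Imbalance (mm) | Bias (mm) | % of 0.25 mm | One-sided type I error | Power |
|---|---|---|---|---|---|
| 0 | any | 0 | 0 | 0.0250 | 0.807 |
| any | 0 | 0 | 0 | 0.0250 | 0.807 |
| 0.1 | 0.1 | 0.005 | 2 | 0.0285 | 0.792 |
| 0.1 | 0.2 | 0.010 | 4 | 0.0324 | 0.775 |
| 0.2 | 0.2 | 0.020 | 8 | 0.0415 | 0.740 |
| 0.3 | 0.3 | 0.045 | 18 | 0.0734 | 0.640 |

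Last row: 0.3/2 × 0.3 = 0.045; 0.045/0.088 = 0.51; 1 − Φ(1.96 − 0.51) ≈ 0.073.

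**4. Simulation check.** No true effect, 64 per group, residual SD 0.5, baseline SD 0.5, correlation 0.6, 4,000 runs per setting.

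| Gap, imbalance | One slope: bias; type I error | Visit-specific slopes: bias; type I error |
|---|---|---|
| 0, 0.3 | 0.0006; 0.029 | 0.0006; 0.027 |
| 0.3, 0 | 0.0001; 0.028 | −0.0002; 0.023 |
| 0.1, 0.2 | 0.0113; 0.031 | 0.0013; 0.025 |
| 0.2, 0.2 | 0.0212; 0.043 | 0.0012; 0.028 |
| 0.3, 0.3 | 0.0446; 0.075 | −0.0003; 0.029 |
| 0.3, 0.3, with 15% of V4 missing | 0.0510; 0.078 | 0.0005; 0.023 |

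The formula is confirmed. These runs use two groups and omit site, severity and the SAP's other covariates.

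**5. Does time since last SRP cure it?** A separate simulation (64 per group, residual SD 0.45, correlation 0.6, 3,000 runs) added that term. At gap and imbalance 0.2 the bias was 0.020 to 0.021 mm with it and 0.019 to 0.020 mm without; at 0.3 each, 0.045 to 0.047 and 0.044 to 0.045 mm. Visit-specific slopes gave 0.000 to 0.002 mm. The SD of the estimates was 0.081 to 0.087 mm with one slope and 0.081 to 0.085 mm with two.

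**The case against.** The strongest reply is that both inputs lack a source and may be small.

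- **Slope gap.** Eight weeks is an upper limit for SRP, and section 4 of the protocol starts it on teeth of at least 4 mm and on the most diseased tooth, which works against the deepest teeth healing least by V3. A late finisher also has the same deficit in healing days at both visits, so if healing were linear in time, the delay alone would create no gap. A gap by that route needs healing to level off. Simulating it with exponential healing (assumed total response 1 mm, time constant 15 to 90 days, last SRP on average day 28 and 10 to 28 days later per mm of depth) gave gaps of only 0.01 to 0.13. A reader might infer from the schedule that the slopes must differ; the documents contain no healing curve and do not support that.
- **Imbalance.** Allocation is "IQOS arm:cigarette arm in a 1:1 ratio using a stratified randomization", severity is a stratification factor, and planned non-adherence is 10%, so use groups should largely follow the arms. This limits the imbalance but does not remove it: stratification uses one cut at 5 mm on the worst site, and it balances arms rather than use groups.
- **Existing provisions.** Residual diagnostics, predicted-versus-observed checks and the note on extra covariates could bring the term in. None of them pre-specifies it.

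The first two replies stand as limits on size. They do not show that either quantity is zero.

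**Conclusion.** The concern holds in conditional form. The primary model has no baseline-by-visit term, and the month-6 contrast keeps half the slope gap times the baseline imbalance. Both must be non-zero for any bias. On assumed inputs it is small for modest values (0.005 to 0.020 mm) and becomes material only when both are large (0.045 mm at 0.3 each). The direction is unknown: it could inflate a finding for IQOS or cost power.

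Three stronger readings are tempting and not supported:
- that a baseline difference alone distorts the result: with equal slopes the bias is zero at any imbalance;
- that the comparison of the Full Analysis Set by randomised arm is biased in the same way: chance imbalance averages to zero under randomisation, so this is not a bias in expectation;
- that the SAP treats severity as a main effect only: item 9 interacts it with product use. What is missing is an interaction of any baseline covariate with visit.

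This is an inexpensive safeguard for a comparison of non-randomised groups. It does not show that the planned result will be wrong.

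**What to change.** In protocol 12.6 and SAP 9.5.1.1, add full-mouth PD at V1 by visit and disease severity at V1 by visit as fixed terms. Place them with the covariates that are always kept, outside the backward selection, and write them into the sample code. In the CAL model of SAP 9.5.2.1, use full-mouth CAL at V1 by visit in the same way. Take the month-6 contrast from that model, and record the change in SAP section 7 if the protocol text is left as it is. If the primary model can no longer be changed before unblinding, report this version as a labelled sensitivity analysis.

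The cost is one degree of freedom for the PD term and one for severity. No new data are needed, the simulations showed no loss of precision, and the sample size stays at 64 evaluable and 86 randomised per arm.
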